5.2.7 Enrollment, Screen Failures, and Study Completion

Patients are considered enrolled from time consented to participate until designated as a screen failure or have either been discontinued from the study or completed it. A screen failure is a patient who signed informed consent, but then was determined to be ineligible or withdraws from the study. Subjects are considered to have completed the study when they are followed through day 60 or have had an adverse event or death occurred prior to day 60.

Day -1 to 0 Baseline:

- A. Subject informed consent (obtained before performing study related activities)
- B. Baseline Evaluation at screening.
 1. Demographics (Age, sex ethnicity, race)
 2. Medical history (timing of exposure to COVID-19 source patient, acute and chronic medical condition, medications, allergies.) Any medical condition arising after consent should be recorded as AE.
 3. COVID-19 symptom screen (fevers, cough, shortness of breath, diarrhea, anosmia), onset of symptoms, source of contagion
 4. Vital signs

5. COVID-19 testing (RT-PCR) from nasopharyngeal, throat, tracheal aspirate or bronchoalveolar lavage and stool (optional) samples
6. Blood typing, CBC with differential, comprehensive metabolic panel
7. Serological testing: anti-SARS CoV-2 titers
8. Immune testing samples
9. Urine or serum pregnancy test for females of childbearing potential. Results from laboratory tests obtained up to 7 days before enrollment may be used for the pregnancy test.
10. Determination of eligibility as per inclusion/exclusion criteria, age, consent, positive for COVID-19, respiratory symptoms within 72 hours of admission

DAY 0 Baseline and Infusion:

1. Study Plasma Administration: 1-2 units of plasma will be transfused over 1-2 days. Time at start and end of infusion will be recorded and vital signs will be measured immediately prior to infusion, 10-20 minutes after start of infusion, at completion of infusion and 30-60 minutes after the end of the infusion
2. COVID-19 symptom screen (fevers, cough, shortness of breath)
3. Assessment of clinical status (8-point ordinal scale)
4. New medical conditions, concomitant medication, AE evaluation
5. Physical examination
6. COVID-19 testing (RT-PCR) from nasopharyngeal, throat or stool (optional) samples
7. Blood typing, CBC with differential, comprehensive metabolic panel, C-reactive protein
8. Serological testing: anti-SARS CoV-2 titers
9. Blood for Immune evaluations of cellular and humoral immunity (4 green tops, 30-40 milliliters).

Day 1-7 (or for duration of hospitalization)

1. Vital signs daily (including supplemental oxygen requirements)
2. COVID-19 symptom screen (fevers, cough, shortness of breath)
3. Assessment of clinical status (8-point ordinal scale)
4. New medical conditions, AE evaluation
5. Physical examination
6. CBC with differential, comprehensive metabolic panel, CRP daily

Days 0, 4 (\pm 1 day), 7 (\pm 2 day), 14 (\pm 3 days), 21 (\pm 3 days), and 28 (\pm 3 days):

1. SARS-CoV-2 PCR from oropharyngeal or nasopharyngeal swabs: Day 0, 4, 7, 14, 21 and at any time when there is clinical suspicion for COVID-19.
2. Serum or plasma antibody titer to SARS-CoV-2: Day 0, 7, 14, and 28
3. Blood for immune evaluations of cellular and humoral immunity before CIP infusion (day 0) and 7, 14, and 28 days after CIP infusion (4 green tops, 30-40 milliliters). Immune testing may be done at any time if the PI determines there is a need to evaluate acute immune responses (cytokines/chemokines levels).

Key issues to consider follow up by phone, alive, at home, in hospital (ICU or not), on supplemental O₂ or not, back to work, fully and partially

- COVID-19 symptom screen (fevers, cough, shortness of breath)
- Assessment of clinical status (8-point ordinal scale)
- New medical conditions, AE evaluation

Day 60 (\pm 7 days):

1. COVID-19 symptom screen (fevers, cough, shortness of breath)

2. Assessment of clinical status (8-point ordinal scale)
3. New medical conditions, AE evaluation

One year (\pm 1 month) - *optional*

- 1. Serum or plasma antibody titer to SARS-CoV-2**
- 2. Blood for immune evaluations of cellular and humoral immunity**
- 3. CBC with differential, Comprehensive metabolic panel, PT/INR, PTT, Quantitative immunoglobulins**
- 4. Interval medical history**
- 5. Subject questionnaires regarding health status**

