2. Age \geq 18 years of age
3. No receipt of convalescent plasma

Immunologic Controls:

1. PBMCs with 5-10 million cryopreserved cells per specimen present in the prospective COVID 19 Biorepository
2. Serum or plasma 500 UI each from up to 50 patients present in the COVID-19 Biorepository

Assessment and Data Acquisition:

1. Baseline: Age, sex, comorbidities, date of symptom onset, known COVID-19 contact, type of admission to the floor or ICU, APACHE score (ICU scoring system to classify disease severity and mortality risk), SOFA score (mortality prediction score based on organ function), clinical status, vital signs including temperature, respiratory rate, oxygen saturation, oxygen requirement, neutrophil count, lymphocyte count, CRP, chest x-ray, chest CT, location in hospital.
2. Safety and efficacy: Day 0 (baseline), 1, 2, 3, 4, 7, 14, 21, and 28 and once at day 60.
3. SARS-CoV-2 PCR from OP or NP swabs: Day 0, 4, 7, 14 and at any time when there is clinical suspicion for COVID-19.
4. Outcome measures: increased O₂ requirement (PaO₂/FiO₂ ratio or SpO₂/FIo₂), supplemental oxygen strategy (nasal cannula, high flow nasal cannula, noninvasive ventilation, intubation and invasive mechanical ventilation, rescue ventilation i.e. neuromuscular blocking agents, prone positioning, corticosteroids, ECMO), vasopressors, renal support, ICU LOS, ICU mortality, hospital LOS, hospital mortality, 28 day mortality.
5. Serum or plasma antibody titer² to SARS-CoV-2: Day 0, 7, 14, and 28. Samples from the COVID-19 Biorepository from non-transfused patients will be assayed at two similar timepoints as Immunologic Controls.
6. Blood for immune evaluations of cellular and humoral immunity before CIP infusion (day 0) and 7, 14 and 28 days after CIP infusion. Immune testing may be done at any time if the PI determines there is a need to evaluate acute immune responses (cytokines/chemokines levels). Samples from the Prospective COVID-19 Biorepository from non-transfused patients will be assayed at two similar timepoints as Immunologic Controls.
7. "Clinical controls" will have all relevant datapoints collected via chart review (i.e. biospecimens will not be collected prospectively)

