10.9 Subject Status Definitions

- Enrolled: All subjects who sign an informed consent will be considered enrolled on the study. All subjects consented on the study must be entered into Clinical Trials Office Database.
- Screen Failure: A subject who is withdrawn or discontinues from study screening prior to being on study is considered a screen failure. Screen failures are not considered a study accrual and will be replaced. Note: The IRB defines any individual that has signed an informed consent as an enrollment in this study and so screen failures should be reported to the IRB with enrollment numbers.
- On-Study: A subject is considered on-study on the date when the study team has confirmed the subject has met all of the inclusion and none of the exclusion criteria, and the treating physician/surgeon or study PI has signed off on the confirmation.
- On-Treatment: A subject is considered on-treatment on the date that they receive the first study treatment. A subject who is withdrawn or discontinues from the study after receiving at least 1 infusion is considered a discontinuation and will not be replaced.
- On Follow-up: A subject is considered on follow-up on the date that they have met any of the criteria in section 4.0.
- Off-Study: A subject is considered off-study if they are removed from the study for any of the reasons listed in section 4.0 or if they have completed all study assessments through follow-up.
- Immunologic Controls: A subject for whom biospecimen is obtained from the COVID-19 Biorepository.

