12.8 Reporting Interval

All AEs and SAEs will be documented from the first administration of study product and for the following 7 days or until un-enrollment from the study, whichever comes sooner. All AEs and SAEs will be followed until resolution even if this extends beyond the study-reporting period. Resolution of an adverse event is defined as the return to pre-treatment status or stabilization of the condition with the expectation that it will remain chronic.

At any time after this 7 day period, if the investigator becomes aware of a SAE that is suspected to be related to study product

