12.9 Investigator's Assessment of Adverse Events

The determination of seriousness, severity, and causality will be made by an on-site investigator who is qualified (licensed) to diagnose adverse event information, provide a medical evaluation of adverse events, and classify adverse events based upon medical judgment. This includes but is not limited to physicians, physician assistants, and nurse practitioners.

Laboratory abnormalities will be reported as AEs if there is a 2 times standard deviation increase above baseline.

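### Section 5.2.7 counts any adverse event before day 60 as study completion, which contradicts the visit schedule and the off-study definition and puts later endpoint data at risk

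*Combined protocol and SAP*

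**What the plan says.** Section 5.2.7 gives three routes to completion. Subjects have completed when they are "followed through day 60 or have had an adverse event or death occurred prior to day 60". Nothing restricts the adverse event by grade, seriousness, relatedness or timing within the 60 days. The same paragraph treats a patient as enrolled "until designated as a screen failure or have either been discontinued from the study or completed it", so completion ends enrolled status.

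The trigger is wide. Section 5.2.7 adds "Any medical condition arising after consent should be recorded as AE", and section 12.9 adds "Laboratory abnormalities will be reported as AEs if there is a 2 times standard deviation increase above baseline".

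Section 12.8 documents AEs and SAEs from the first study product "for the following 7 days or until un-enrollment from the study, whichever comes sooner". It also says "All AEs and SAEs will be followed until resolution even if this extends beyond the study-reporting period".

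Other sections set follow-up without regard to AEs. The Summary lists "Safety and efficacy: Day 0 (baseline), 1, 2, 3, 4, 7, 14, 21, and 28 and once at day 60". Section 10.9 calls a subject off-study if "removed from the study for any of the reasons listed in section 4.0 or if they have completed all study assessments through follow-up".

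**The concern.** The trial's main decision is a count of ICU transfers in 29 patients, so the protocol has to be clear about who is still under observation and for how long. Read literally, 5.2.7 makes a subject complete after a mild fever or rash during the infusion. That subject is then no longer enrolled, and 12.8 closes the AE record. An ICU transfer or death some days later would follow completion, and 5.2.7 gives no instruction to record it.

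Three things would be at stake:

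- **ICU transfer and 28-day mortality.** Events that follow an earlier AE could be missed.
- **Cumulative incidence of SAEs, and Grade 3 or 4 AEs.** These could shrink towards a first-event count.
- **Antibody and immune measurements at days 7, 14 and 28.** These could be treated as no longer required.

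Section 10.9 ought to settle when a subject leaves the study. For the reasons for removal it points to section 4.0, which contains only eligibility criteria.

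**Working it through.** **Step 1: set the sections side by side.**

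| Section | What it implies after an AE on, say, day 0 |
|---|---|
| 5.2.7, completion sentence | Subject has completed and is no longer enrolled |
| 12.8 | AE/SAE documentation stops at un-enrollment if that precedes 7 days; existing AEs are followed to resolution |
| Summary, 5.2.7 visit list, Table 1 | Visits continue to day 28 and day 60, with no AE-free condition |
| 10.3 | All Table 1 assessments should be completed |
| 7.2 | 28 days of follow-up are allowed to obtain the primary endpoints |
| 10.8 | Everyone who received any study treatment has immune assessments, at days 0, 7, 14 and 28 |
| 10.9 | Off-study only after all assessments, or on removal for a section 4.0 reason |

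The first row cannot be squared with the last five, and no order of precedence is stated. Two details limit the reach of 12.8. It does not define un-enrollment, so equating that with completion is a reading, though the natural one given 5.2.7. And its window closes at 7 days anyway, so the completion clause can shorten it only within that first week. Following an AE to resolution covers that AE, not a later ICU transfer, death or titer.

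**Step 2: the section 4.0 reference.** Section 4.0 holds inclusion and exclusion criteria, among them mechanical ventilation and oxygen above 6 L/min. Section 5.2.6 confines removal on those two grounds to the period before infusion; 10.9 carries no such limit.

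**Step 3: reproduce the plan's own figure.** Sections 7.1 and 9.1 give 29 evaluable patients, 80% power, 50% versus 25%, two-sided 0.05, and rejection at 8 or fewer ICU admissions. By the one-sample normal approximation,

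n = [(1.96 × √(0.5 × 0.5) + 0.8416 × √(0.25 × 0.75)) / 0.25]² = 28.92, rounded up to 29, with power 80.1% at n = 29.

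The plan's N therefore reproduces. The exact binomial for the stated rule gives P(X ≤ 8 | 29, 0.50) = 0.0121 in one tail (0.0241 doubled) and P(X ≤ 8 | 29, 0.25) = 0.7125. That power shortfall is a separate matter.

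**Step 4: illustrate the effect of missed transfers.** The documents give no figure for the share of transfers that might follow an earlier AE, so the share m is assumed. Suppose missed transfers count as non-events and the denominator stays at 29. The counted rate under no effect is then p = 0.5 × (1 − m), and the chance of meeting the rule is P(X ≤ 8 | 29, p).

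| Assumed m | Counted rate | P(8 or fewer of 29) |
|---|---|---|
| 0% | 50% | 1.2% |
| 5% | 47.5% | 2.3% |
| 10% | 45% | 4.3% |
| 20% | 40% | 11.9% |
| 30% | 35% | 26.5% |
| 40% | 30% | 47.9% |

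**Step 5: the alternative handling.** The rule applies to evaluable patients, a term the protocol does not define. Suppose affected subjects drop out of that set at random, and the cutoff is reset to the largest count with one-tail null probability at most 0.025. Exact power at 25% then falls from 71.3% (n = 29) to 68.5% (n = 26, cutoff 7), 65.4% (n = 23, cutoff 6) and 61.7% (n = 20, cutoff 5). Type I error is not inflated in that case.

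**The case against.** The strongest reply is that the sentence defines a status and does not order anyone to stop. The visit schedule and sections 10.3, 10.8 and 7.2 all point to continued assessment, and section 8.1 lists mortality at 28 and 60 days. Staff who follow Table 1 would lose nothing. The literal reading also gives odd results: since 5.2.7 records any condition arising after consent, a symptom before infusion could complete a subject who has not been treated. That suggests the clause was not meant to work this way. All of this stands. It shows that the likely intent differs from the text, but it does not remove the contradiction.

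A reader might infer that 5.2.7 actually ends follow-up, and does so before the primary endpoints can be seen in the sickest patients. The documents do not support that. A death before day 60 is itself a completion event and is recorded if it comes first. An ICU transfer that is the first AE is likewise captured. Only events after an earlier AE are exposed. Nor does the clause single out the sickest: it covers minor and laboratory AEs, and a trigger that many patients would meet early is not clearly selective for deterioration. AEs may well cluster in patients who are worsening, but the protocol gives no data on this.

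The objection that the size of the bias is unsourced is also right. It depends on an assumed share and on an assumed handling of missed transfers.

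**Conclusion.** The contradiction is real and should be corrected. The completion wording in 5.2.7 conflicts with the schedule, Table 1 and sections 7.2, 10.3, 10.8 and 10.9. Followed as written, it would give a wrong account of who is still enrolled and could cut short the recording of ICU transfers, deaths and AEs that follow an earlier AE.

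The size cannot be derived from the documents. If missed transfers were counted as non-events, the bias would favour plasma; a 20% loss would take the one-tail error from 1.2% to 11.9%. If the subjects were instead dropped at random, the cost would be power. A reader might conclude that the primary objective cannot be answered. That goes too far, because the scheduled visits, if carried out, supply the data.

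**What to change.** - **Section 5.2.7:** delete the adverse-event alternative, so that completion means follow-up through day 60 or death.
- **Section 5.2.7, added sentence:** ICU transfer and vital status through day 28, and the scheduled safety data, are collected for every infused subject whatever the AE history, unless the subject withdraws consent, is lost to follow-up or is withdrawn under 5.3.
- **Section 10.9:** replace the section 4.0 reference in the off-study definition with 5.2.6 (before infusion only) and 5.3. The on-follow-up definition carries the same reference and should be checked at the same time.
- **Section 5.3:** leave it unchanged. It lets the investigator withdraw a subject for non-compliance, harm to the subject or data integrity, so the new text should not name consent withdrawal and loss to follow-up as the only exits.

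The cost is protocol wording. Day 28 and day 60 contacts are already scheduled for every recipient, so no new visits are needed.

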5.3 Subject Withdrawal

1. Subjects can terminate study participation and/or withdraw consent at any time without prejudice.
2. The investigator may withdraw subjects if they are lost to follow up, non-compliant with study procedures or if the investigator determines that continued participation in the study would be harmful to the subject or the integrity of the study data
3. Discontinuation of the study: the study sponsor, FDA and IRB all have the right to terminate this study at any time

5.4 Concomitant medications will be documented on the CRF

- Prescription medications
- Over the counter medications
- Herbal treatments/nutritional supplements
- Blood products

5.5 Known potential benefits

A key potential benefit is treatment for established infection. Convalescent plasma would be administered to those with clinical disease in an effort to reduce their symptoms and mortality. Based on the historical experience with antibody administration, it can be anticipated that *antibody administration relatively early in the course of disease would be more effective in preventing disease progression than in the treatment of established severe disease.*

Given that historical and current anecdotal data on use of convalescent plasma suggest it is safe in coronavirus infection, the high mortality of COVID-19, particularly in elderly and vulnerable persons, suggests that the benefits of its use in those at high risk for poor outcome and or with early disease outweigh the risks. However, for all cases where convalescent plasma administration is considered, a risk-benefit assessment must be conducted to assess individual variables.

5.6 Known potential risks

5.6.1 Antibody-Mediated Enhancement of Infection (ADE)

The theoretical risk involves the phenomenon of antibody-mediated enhancement of infection (ADE). ADE can occur for several viral diseases and involves an enhancement of disease in the presence of certain antibodies. For coronaviruses, several mechanisms for ADE have been described and there is the theoretical concern that antibodies to one type of coronavirus could enhance infection to another viral strain¹¹. It may be possible to predict the risk of ADE of SARS-CoV-2 experimentally, as proposed for MERS. Since the proposed use of convalescent plasma in the COVID-19 epidemic would rely on preparations with high titers of antibody against the same virus, SARS2-CoV-2, ADE may be unlikely. The available evidence from the use of convalescent plasma in patients with SARS1 and MERS¹² and anecdotal evidence of its use in patients with

COVID-19¹³, suggest it is safe. Nevertheless, caution and vigilance will be required in for any evidence of enhanced infection. Alterations in serum potassium and calcium levels can occur with these patients.

5.6.2 Attenuated Immune Responses

Another theoretical risk is that antibody administration to those exposed to SARS-CoV-2 may avoid disease but modify the immune response such that those individuals mount attenuated immune responses, which would leave them vulnerable to subsequent re-infection. In this regard, passive antibody administration before vaccination with respiratory syncytial virus was reported to attenuate humoral but not cellular immunity¹⁴. We will investigate this unexpected potential as part of the clinical trial by measuring immune responses in those exposed and treated with convalescent plasma to prevent disease. If the concern proved real these individuals could be vaccinated against COVID-19 when a vaccine becomes available. *These concerns seem modest compared to the possibility of limiting the duration and severity of disease, and avoiding complications like mechanical ventilation, ARDS, sepsis, and death.*

5.6.3 Transfusion Transmitted Diseases

Finally, there are risks associated with any transfusion of plasma including transmission of transfusion transmitted viruses (e.g. HIV, HBV, HCV, etc.), allergic transfusion reactions, anaphylaxis to transfusion, febrile transfusion reaction, transfusion related acute lung injury (TRALI), transfusion-associated cardiac overload (TACO), and hemolysis should ABO incompatible plasma be administered. In order to minimize the risks of disease transmission, pathogen reduction techniques will be utilized to prepare the plasma. In addition, donors will fulfill all donor requirements for whole blood donation and frequent apheresis plasma donation with the exception of recent illness, in this case COVID-19 infection.

6.0 PREPARATION OF CONVALESCENT IMMUNE PLASMA

The plasma product will be collected from **directed**-donors or anonymous donors from the American Red Cross, New York Blood Center, or other local blood donation facility 28 days after symptom resolution. Antibody titers may be assessed by prescreening 21 days after symptom resolution with an anti-SARS-COV-2 titer of preferably >1:64 and/or by measuring titers from the infused plasma. We will use an FDA-approved test to measure antibodies, such as the Ortho Clinical Diagnostic or equivalent test for total IgG, IgM, and IgA directed at COVID-19 spike protein. Donors may be recruited from COIV-19 Screening Clinics, Employee Health Clinics within the health system and by social media advertising. Per current FDA recommendations and ARC practices, it is assumed that by day 28 after symptom resolution, that there will be no viable viral COVID-19 in the circulation. Otherwise the donor will fulfill all of the standard donor criteria for plasma donation.

Donors and samples will have been screened for transfusion-transmitted infections (e.g. HIV, HBV, HCV, WNV, HTLV-I/II, T.cruzi, ZIKV) both through the use of the uniform donor questionnaire and FDA mandated blood donor screening tests. Plasma will have been collected by the ARC or local donation site using standard apheresis technology and in accordance with standard FDA and blood bank protocols. The CIP will be in standard plasma unit bags with storage, handling, and release per blood bank guidelines. The patient will receive 1-2 units of anti-SARS-CoV-2 convalescent plasma.

Table Treatment Schedule	I: Screen n	Baseline	Transfusion	Follow-up							
				1	4±1	7±2	14±3	21±3	28±3	60±7	1 year
Day	-1 to	0	0	1	4±1	7±2	14±3	21±3	28±3	60±7	1 year

	0				day	day	days	days	days	days	±1 month ⁵
Eligibility											
Informed consent	x										x
Demographic and Medical history	x										x
COVID-19 symptom screen	x										
SARS-CoV-2 RT-PCR for eligibility	x										
Pregnancy test	x										
ABO	x										
Study Drug Administration											
Drug infusion			X								
Study Procedures											
Vital signs ⁴	x	x	Xxxx ³	x	x	x	x	x	x	X	
Physical examination ⁴	x		x	x		x		x		X	
Symptom screen ⁴	x	x	x	x	x	x	x	x	x	X	x
Concomitant medications ⁴	x	x	x	x	x	x	x	x	x	X	
Assessment with 8-point ordinal scale ⁴		x		x	x	x	x	x	x	X	
Adverse event monitoring ⁴		x	x	x	x	x	x	x	X	X	
Health Questionnaire											x
Laboratory testing											
CBC and CMP ⁴		x		x		x	x	x	X	X	X
SARS-CoV-2 RT-PCR (NP or OP)		x			x	x	x	x			
SARS-CoV-2 antibody		x				x	x		x		x
Blood for immune testing		x				x	x		x		x
PT/INR, PTT, Quantitative Immunoglobulins											x

ABO typing may be historical documentation of blood type ²Measured by an anti-SARS-CoV-2 ELISA and serum antibody titer to SARS-CoV-2. ³ Vital signs will be performed pre-transfusion, 10-20 mins after the start of transfusion, at completion and 30-60 mins after the end of the transfusion. ⁴Done daily through Day 7 or until patient is discharged from the hospital, whichever comes first ⁵Optional follow up visit for CIP recipients

